Preliminary Studies Examining Usual Care Services. We examined supports and services received by orphans in TZ and KE using our longitudinal data from POFO. At baseline, nearly half of all POFO study participants in the Bungoma, KE (49%) and Moshi, TZ (42%) regions received at least some support in the form of food, clothing, educational assistance, money, childcare, counseling/emotional support, medical care, and/or transportation. At 36-months, rates of support remained stable in TZ (48%) and increased dramatically in KE (91%), mostly due to the influx of services following political violence (although anecdotal evidence indicates that this high level of support is has not been maintained). Support services were received from community, religious, and government organizations, as well as from friends and family. At the 36-month POFO follow-up, 31% of the KE respondents and 15% of the TZ respondents reported that they were receiving counseling/emotional support. The POFO children in KE also had higher rates of emotional and behavioral needs following the political violence than did those in TZ. Preliminary results from POFO indicate that recipients of support were those with higher emotional and behavioral needs (identified via Strengths and Difficulties Questionnaire, also used in the proposed study, see Table 4) and in worse physical health, suggesting that children with greater needs receive more services. The effectiveness of UC services in improving outcomes is unknown. ACE Africa and TAWREF are aware of the local support services to which participants can and will be referred (in addition to those provided by their own organization), and each have established a local Standard of Care document (see Appendix C for Bungoma, KE example).

3C4. Assessment and Data Collection Procedures

3C4a. Assessment: Children and Guardians. Clinical outcomes are assessed by child and guardian report at baseline, 12-14 weeks post-baseline (i.e., end of treatment for the TF-CBT condition, with a 2-week window), and at a 6- and 12-month follow up, to assess maintenance of any gains. Two trained interviewers at each site conduct all interviews. Interviewers will have minimal contact with lay counselors and will not attend the TF-CBT groups, so the intervention is not contaminated nor are the interviewers biased. The clinical assessment battery reflects what was used in the feasibility study (therefore many of the measures for this proposal have already been translated, back-translated, and approved by the Duke IRB and Kilimanjaro Christian Medical Center, for Moshi, TZ). One change that we believe enhances the assessment battery is inclusion of a locally derived tool to assess daily functioning activities, as other studies have demonstrated functional impairment resulting from CTG⁵³. The locally derived tool will be developed during the first year of the project, in both regions, following standardized qualitative measurement development procedures¹⁰⁵. An interview guide for development of the functioning tool was created during the feasibility study and is approved by the Duke IRB for use in Moshi, TZ (see Table 4 and Appendix A, for the interview guide and an example functioning tool from [name] & [name]'s other research).

3C4b. Assessment: Lay Counselors. In addition to clinical outcomes, we examine implementation factors that may affect clinical outcomes and, by measuring them in this RCT, we establish a benchmark for future implementation efforts. Implementation outcomes, as detailed below, include child and guardian attendance at groups (which may vary across countries; urban vs. rural settings), lay counselors' knowledge and fidelity to TF-CBT, and the lay counselor-supervisor relationship. Lay counselors will complete measures assessing knowledge and the supervisory relationship with the local trainers (see Table 4). These measures are administered to the lay counselors by the project coordinator (PC) in each site via paper and pencil self-report format and will be returned to the PC in a sealed envelope. Self-report fidelity data will involve lay counselors completing the group reports after each TF-CBT group session and emailing these reports to the local trainers and to [name] and [name], within two days of the group. Lay counselors audiorecord all sessions digitally. The electronic files are collected by the PC on a jump drive. Three child and 3 guardian sessions (6 total) will be randomly selected from each group by [name] (remotely) and will then be coded by the data entry person, who also serves as the independent coder and will be trained by Drs [name] and Cohen in TF-CBT coding procedures.

3C4c. Data Collection from Children and Guardians. As in our other research, interviewers who have experience in working with children and a college degree in a field related to data management or social services are selected. Interviewers will undergo one week of training. Interviewers receive training in issues of research confidentiality, protocols, ensuring common understanding of questions, and standard ethical procedures (see Human Subjects for more information and Appendix C for example training documents). Interviewers will not be allowed to begin interviewing until they have been certified by [name] and [name] on all procedures and passed practice interviews (see Appendix C: Interview Training Log).

Our team has established procedures for monitoring interviewers during the RCT that decrease interviewer bias and drift (see Appendix C, Example Shadowing Log). The local PC in each site will shadow each interviewer for at least one child and one guardian interview each month. Interviewers will also be required to shadow a colleague’s interview once per month. Both interviewer and “shadower” independently complete the assessment forms to allow examination of adherence to the protocol. In each case, the “shadower” and interviewer debrief about the interview within 48 hours. Shadowing logs are maintained and reviewed monthly during the M-PI and PC calls.

The primary offices of interviewers and the data entry person and the lay counselors are physically separate so that they do not inadvertently discuss participants, the study condition, or an interview. This physical separation, along with training on the importance of maintaining confidentiality and clear communication of confidentiality to guardians and children, helps ensure non-biased study results. The Lead Investigators in both countries understand the importance of maintaining confidentiality and not contaminating either the intervention or research data by allowing interviewers and counselors to discuss, even casually, their work with participants. Investigators research teams will hold weekly calls with the interview team (via Skype) that are separate from the TF-CBT supervision calls with the local trainers.

3C4d. Recruitment and Screening. All child/guardian participants will be identified by the two partner agencies in Moshi, TZ (TAWREF) and Bungoma, KE (ACE Africa). Children who are orphaned come to their attention through their existing support services (e.g., NGOs, church), from schools, or from other local groups. Staff from the partner agency make the initial contact with any potential participants and ask about willingness to receive information about the study. Children and guardians who are interested participate in a 2-level consent process conducted by the interviewers (see Human Subjects for additional information on recruitment, screening, and consent procedures). The two-level consent is similar to that used in our feasibility study, with added details on randomization, with the first level for screening (e.g., brief assessment of CTG and PTS). **Eligibility criteria** for study participation include: 1) child age between 7-13; 2) single or double orphan; 3) guardian adult (≥ 18 years old) who is willing to participate in either arm of the study and understands the randomization process ; 4) child’s parent(s) died *after* the age of 4 years (to ensure the child remembers the parent) and *before* the last 6 months (to avoid normal distress immediately post-death); and 5) a score of 10 or higher on the CTG measure or a score of 15 or higher on the PTS measure, by either child or guardian report. The inclusion criteria are designed to be broad, include even mild symptoms, but not to include children who do not need intervention. **Exclusion criteria** are few and include: 1) known developmental or cognitive disability, 2) the unwillingness of the child or guardian to be randomized, and 3) the unwillingness of the guardian to attend a 12-week group if randomized to the TF-CBT condition.

If children are eligible and assent and consent are provided, remaining baseline assessment measures are administered (see Table 4) and participants are randomized. Randomization procedures occur prior to the screenings by the local PC and Drs. [name] and [name], reducing any randomization bias. Interviewers have a numbered stack of consent forms that are used in numerical order. Each consent form includes an attached envelope with randomization status (see Human Subjects for more information). Guardian-child dyads randomized to TF-CBT begin the 12-week group protocol within 2 weeks. All dyads are assessed again at 12-14 weeks post-baseline, 6-months, and 12-months post baseline. For all assessment meetings, children and guardians receive a small incentive for participation costing <\$2.50, (e.g., bag of sugar, laundry soap, pen).

Table 4. Study Measures (All Measures are included in Appendix A)

Domain; Respondent ^A	Measures & Indicators	Interval [*]	
Demo-graphics; G	Demographic Survey. We assess pertinent demographic information (e.g., guardian characteristics, years caring for child, home situation) using an established demographics measure from POFO, also used in the feasibility study. † +	BL, 12w, 6M, 12M	
Clinical Outcomes	Posttraumatic Stress; C, G	UCLA PTSD Index for DSM-IV¹⁰⁸ (UCLA PTSD-RI). The 38-item UCLA PTSD RI assesses trauma exposure and PTS symptoms. Response choices for PTS items are 0 - 4. The UCLA PTSD RI demonstrates good convergent validity and good to excellent test-retest reliability. Cronbach’s α in the range of .90. †	BL, 12w, 6M, 12M
	Behavioral Difficulties; G	Strengths & Difficulties Questionnaire¹⁰⁷ (SDQ). The SDQ is a brief behavioral screening survey (ages 3-16) with 25 items on 5 scales (Emotional Symptoms, Conduct Problems, Hyperactivity/Inattention, Peer Relationship Problems, & Prosocial Behavior). Response choices are from 0-2. The SDQ has been shown to have good discriminant validity and acceptable levels of test-retest reliability ¹⁰⁸ and a Cronbach’s α of .73 ¹⁰⁹ . †	BL, 12w, 6M, 12M
	Childhood Traumatic Grief, C	The UCLA Trauma Psychiatry Service Grief Inventory , (TPSG) is a 10-item measure that includes a subset of the items on the Expanded Grief Inventory ¹¹⁰ and is used to assess CTG symptoms. The scale has demonstrated moderate - high levels of internal validity, and has been used successfully with children aged 6 and older. †	BL, 12w, 6M, 12M
	Depression, C	Short Mood and Feelings Questionnaire¹¹¹ (SMFQ). The MFQ has 13 items and assesses depressive symptoms over the past 2 weeks. Each item is assessed on a 0 – 2 scale. Scores over 11 are considered clinically significant. The SMFQ has acceptable psychometric properties with a Cronbach’s α of 0.87. †	BL, 12w, 6M, 12M

	Child-Guardian Relationship; G	Child-Parent Relationship Scale ¹¹² (CPRS). The CPRS is an unpublished measure that includes 15 items that assess the warmth of the child-guardian relationship from the guardian's perspective. It has been used successfully in the POFO study with acceptable levels of reliability and validity. Items are scored from 1-5. +	BL, 12w, 6M, 12M
	Child Functioning; C	Child and Adolescent Functioning . This locally derived tool will be developed during year 1 of the project, following established procedures ¹¹³ . As in [name]'s other work, our team will conduct free list interviews to identify common areas of functioning for children in KE and in TZ (see Interview Guide and example measure in Appendix A). These qualitative interviews result in a list of approximately 10 -15 common activities/tasks (1 for boys, 1 for girls, for each country). Interviews will be conducted by study interviewers.	BL, 12w, 6M, 12M
Other	Services Received; G	Receipt of Support Services . To measure services received by both conditions, we utilize a set of questions from POFO that have been validated and used in both Moshi, TZ and Bungoma, KE to assess potential supports for children and guardians from a range of formal and informal sources and an interview format adapted from the Child Status Index (CSI) to query the guardian about all services received in the 12 CSI factors. +	BL, 12w, 6M, 12M
Implementation Outcomes	Objective Fidelity; RC	TF-CBT Checklist Scoring Sheet—TZ Group Version . The original TF-CBT Checklist Scoring Sheet, used in prior TF-CBT studies and has a well developed coding manual ¹¹⁴ . The intraclass correlations for the parent and child sessions were .80 and .79, respectively. Our team has revised this coding measure for coding group delivery of TF-CBT, based on the 12-week protocol used in the feasibility study. The coding measure has been piloted by the feasibility study lay counselors. Inter-rater reliability was acceptable. Our team is currently refining and testing this measure (to be completed 9/2011). As this measure is under revision, the original is included in the Appendix.	3 random selected sessions/group
	Self-report of Fidelity, Attendance; LC	TF-CBT Group Report—Child and Guardian Forms . These group report forms were developed for lay counselor self-report of fidelity to TF-CBT. It allows for self-report of (1) components covered for each group; (2) time spent on each topic; (3) notes on each component; (4) participant attendance; (5) short subjective report on response of each participant (child or guardian, depending on the form). Examples of 6 groups are included in Appendix A. †	Each TF-CBT group
	Acceptability; G	Exit Interview Guide . We plan to use the exit interview that was used in the feasibility study to assess acceptability and appropriateness. The exit interview solicits guardian feedback about the TF-CBT intervention. †	12w, TF-CBT only
	Counselor Knowledge, LC	TF-CBT Knowledge Test . In collaboration with [name], our team has developed a short TF-CBT knowledge test that asks about specific TF-CBT components in which lay counselors are trained and are provided in the TF-CBT group. This test was piloted by the feasibility study lay counselors (N=3), who performed at 95%, collectively, on the test.	Post-T [#] ; Post C1
	Supervisory Relationship, LC	Supervision Alliance Scale ¹¹⁵ (SAS). The SAS has 12 items; drawn from two scales ^{116 117} . The 12-item measure assesses the counselor-supervisor relationship and has demonstrated predictive value for burnout and turnover intention and has a Cronbach's α of .95 ¹¹⁵ .	Post C1; Post C2
[^] C= Child, G=Guardian, LC=Lay Counselor; RC: Research Coder (i.e., Data entry person) [*] BL = Baseline; 12w = 12-14 weeks; 6M = 6 months; 12M = 12 months [#] Post-T = Post-Training; Post C1: after delivery of one 1 cycle of groups (2 groups); Post C2: after delivery of 2 nd cycle of groups [†] Measure used in the TF-CBT for CTG Feasibility Study ⁺ Measures used in POFO (both TZ and KE)			

3C5. Data Analysis Plan

Basic data screening procedures will be conducted (e.g., means, standard deviations, skewness, plotting relationships) to screen for errors and explore normality, linearity, form, and outliers. Data will be transformed as appropriate. We will confirm the assumption of randomization at baseline by testing cohort differences in outcome variables (i.e. symptoms), history of traumatic events and basic demographics (i.e. gender and age). Minor differences will be controlled for in statistical models as described below. Statistical analyses for the main aims will be conducted using the SPSS¹¹⁸, Stata¹¹⁹ and Multilevel/Hierarchical Level Modeling¹²⁰ (MLM/HLM) software programs. HLM allows for the presence of missing data at Level 1 (such as when participants are lost to follow-up) appropriately adjusting for data missing at random, particularly when covariates associated with missingness are included in the statistical model¹²¹.

3C5a. Overview of Modeling Approach. Hypotheses related to Aim 1 will be tested using MLM (i.e. HLM, random coefficient models, mixed effects models), which are a powerful and flexible class of analytic approaches that allow for the analysis of non-independent data. MLM allow researchers to account for nesting within different data structures and to explicitly model effects across nested groups. For the current study, the outcome data will be observations of clinical outcomes at multiple time points, nested within children, who are also nested within TF-CBT groups (for the TF-CBT condition). Not accounting for the fact that some children are treated in the same treatment group, for example, could lead to biased estimates. The MLM approach reduces Type I errors caused by violating assumptions of independence, allows time-varying assessments and increases power by utilizing information from multiple time points in a single model.

We will test hypotheses through a standard approach to model-building, focusing on creating parsimonious explanatory models through progressive taxonomies as follows^{122,123}. An unconditional model (i.e. one without predictors) of the outcome will be fitted first, which allows specification of the random effects, which in turn provides an estimation of the amount of interdependence at each level of clustering. For longitudinal models including multiple time points (i.e. client outcomes from baseline to follow up assessments), an unconditional growth model will be fit to identify time trends and inter-individual variance in trends. We will next test the effects of the primary variable of interest (e.g., condition assignment, or therapist fidelity to treatment model) on the outcome in a conditional model (i.e., one with predictors). Finally, theoretically relevant covariates will be

added to determine the robustness of the main effects. Relative goodness-of-fit for each successive model will be evaluated using likelihood ratio tests and deviance statistics.

3C5b. Primary Analyses

Aim 1. Test the effectiveness of a group model of TF-CBT for orphaned youth in two East African countries, including any variation by child age and gender.

Hypothesis 1: Children in the TF-CBT condition will demonstrate greater reductions in symptoms and greater improvement in overall functioning and the child-guardian relationship.

These analyses focus on whether TF-CBT produces significant reductions in symptoms (i.e. CTG, PTS, depression, behavioral problems) or improvement in functioning, or the child-guardian relationship compared to UC. Hypotheses will be tested in two ways using MLM. First, we test whether the TF-CBT condition differs from the UC condition at 12-weeks (i.e., end of TF-CBT). This hypothesis will be tested with a simple 2-level MLM, predicting the observed outcome (by child or guardian report) at 12-weeks, while accounting for clustering of individuals within TF-CBT groups, for the TF-CBT condition. The general Level 1 equation, which models individual differences in symptoms at 12-weeks, would be as follows:

Level 1:	$Symptoms_{ig} = B_{0g} + B_{1g}PreSx + B_{2g}Cov + e_{ig}$
Level 2:	$B_{0g} = \pi_{00} + \pi_{01}Treatment + r_{00}$ $B_{1g} = \pi_{10} + r_{00}$ $B_{2g} = \pi_{20}$

For example, where the outcome is the level of symptoms for a given client i in group g ; B_{0g} (the intercept) represents the average 12-weeks level of symptoms for all children in a given group g , B_{1g} is the effect of pre-treatment symptoms, B_{2g} is the effect of

child/guardian-level covariates (such as demographics: child age, gender), and e_{it} represents residual variance in the outcome for individual i in group g . If randomization was effective, the effects of pre-treatment symptoms may be ignored. The Level 2 equations represent how the coefficients at Level 1 are distributed across treatment groups. Both the intercept and the effects of pre-treatment symptoms (if needed) would be specified as random variables, which would allow their effects to differ across treatment groups. The level 2 equation would follow the general form of $B_{0g} = \pi_{00} + \pi_{01}Treatment + r_{00}$, which uses condition-level variables (such as assignment to TF-CBT or UC) to predict how effects differ. Thus the hypothesis that group-based TF-CBT produces significant improvements in symptoms over the UC condition would be tested by evaluating the significance of π_{01} above, which tests the effects of condition assignment on 12-week symptoms.

To test how TF-CBT influences trajectories of symptoms over time (e.g., 6-months, 12-months), analyses may be expanded to incorporate multiple times of assessments by adding a third level to the above model to test a growth curve model in the MLM framework. Because there are expected to be no differences across conditions at pre-treatment, the intercept could be fixed to the final time point (12-months), allowing two related but distinct questions to be tested: (1) does TF-CBT predict lower levels of symptoms at 12-months; and (2) does TF-CBT produce greater changes (reductions) in symptoms over time than receipt of usual care? The general Level 1 equation would then represent an individual's level of symptoms at a given time point, Level 2 equation would represent individual differences in the Level 1 equation, and Level 3 would represent group differences in the Level 2 equations. Thus the new Level 1 equation would be: $Symptoms_{itg} = B_{0ig} + B_{1ig}Time + e_{itg}$, representing Symptoms at time t for individual i in group g , B_{0ig} being the level of symptoms at Time 0, and B_{1ig} being the effects of Time on symptoms (i.e. the rate of change in symptoms over time). Both the intercept and slope would be allowed to randomly vary across individuals, allowing their prediction from individual level variables (such as pre-treatment symptoms or covariates). For example, the Level 2 equation for the effects of Time would be $B_{1ig} = \pi_{00} + \pi_{01}Cov + r_{00}$. Finally, effects at Level 2 would also be allowed to randomly vary across groups, allowing us to model the effects of condition on the level of symptoms at the final time point, and on the rate of change over time.

It may be that there are significant individual differences in symptoms at 12-weeks, but that these differences do not continue to increase or are not maintained. The hypothesis of decreasing gains for the TF-CBT condition would be tested by adding a quadratic component to the linear growth model. Specifically, the quadratic effect (of time, represented as $time^2$) would test whether there are decelerations in the rate of change in symptoms from baseline to the 12 month outcome, and whether there are individual differences in those decelerations.

Aim 2. Examine any differences in clinical or implementation outcomes for country (TZ; KE) or setting (urban, rural), including differences in receipt of usual care.

These aims would be tested by adding country and rural or urban setting as predictors at Level 2. These analyses would test whether country or setting explain between-condition differences in treatment outcomes at

a specific time point, and for the growth models, whether they explain differences between conditions in the rate of change over time.

Aim 3. Examine the impact of implementation factors (e.g., TF-CBT fidelity, lay counselor-supervisor relationship, child/guardian attendance) on outcomes.

Analyses for Aim 3 will focus on how implementation variables (such as attendance, fidelity, provider knowledge) are related to outcomes at 12-14 weeks (end of TF-CBT) and at the follow-ups. These analyses will be restricted to those in the TF-CBT condition. These Aims are tested by expanding the models described in Aims 1 and 2, above, to include implementation variables at both the individual level (such as attendance) and the group level (TF-CBT fidelity). For example, MLM equations that look at implementation effects on post-treatment levels of symptoms could be:

Level 1:	$Symptoms_{ig} = B_{0g} + B_{1g}PreSx + B_{2g}Cov + B_{3g}Attendance + e_{ig}$
Level 2:	$B_{0g} = \pi_{00} + \pi_{01}Fidelity + r_0$ $B_{1g} = \pi_{30}$ $B_{2g} = \pi_{30}$ $B_{3g} = \pi_{30} + r_2$

These models test how attendance during treatment and fidelity of the treatment provider influence symptoms at 12-weeks and at follow-ups, treating the intercept and the effects of attendance as random effects, and the

effects of pre-treatment symptoms and covariates as fixed effects.

3C5c Power. Power analyses were conducted using Optimal Design 2.0¹²⁴. A primary concern when estimating power in HLM focuses on the Interclass Correlation Coefficient (ICC) for providers, as providers are nested within conditions. Higher positive ICCs result in less statistical power, and few estimates of provider ICCs for fidelity to treatment are available. A review of 20 studies predicting client functioning found provider ICCs clustering from -0.1 to .06¹²⁵. Because precise estimates for ICCs are unknown, we examined ICC thresholds within a range of effect sizes (with .05 Type I error rate, power of .80, 8 children per TF-CBT group; 320 children total). Estimates did not include the effect of covariates which, if moderately correlated with the outcome variable, will increase statistical power. Therefore, these estimates present a conservative estimate. Our primary hypothesis test (i.e. differences at 12-weeks between TF-CBT & UC) is sufficiently powered ($1-\beta = .80$) to detect small effects (.35) with ICCs up to .15, moderate effects (.50) with ICCs up to .30, and all conceivable large effects. For detecting condition differences in terms of the linear or quadratic slope, analyses suggested that the proposed *N* has power ($1-\beta = .80$) to detect effects as small as .29 on slopes. Finally, for Aim 3, the current sample of 320 individuals in the TF-CBT condition, the current study is sufficiently powered to detect small (.21) effects of individual implementation variables on outcomes, but with only 20 clusters (i.e., groups) the study will have less power to detect all but large effects of group-level variables (e.g., fidelity).

3C6. Rationale of Choices Made in the Research Design. Our team carefully considered various design and methodological challenges, our rationale for various decisions is discussed here.

Comparison Condition. Our team considered a range of comparison conditions, including another active treatment arm (12-week social support group) to control for intervention time and a waitlist control. We decided to use a UC comparison group to test differences from services usually received in LAMICs, given scarcity of resources. We considered allowing children and adolescents in the control group to receive the TF-CBT intervention at 6 months (which would preclude examining outcomes at 1-year), but decided against this so that we could examine whether provision of TF-CBT (short-term, but still time-intensive; 12-weeks, 15 sessions) has a lasting impact on clinical outcomes, the child-guardian relationship, and child functioning.

Training and Supervision of Lay Counselors. The counselors in our pilot study were directly trained and supervised by TF-CBT and mental health experts. We decided not to replicate this model of training and supervision in the proposed RCT because (1) there are sufficient findings supporting the ability of local, lay supervisors to supervise lay counselors and (2) our interest is in moving towards increased local responsibility. Therefore, it is necessary to examine effectiveness of TF-CBT, and other mental health interventions, under conditions that are more likely to build sustainability.

3C7. Hazardous Procedures/Materials. None are planned or expected.

3C8. Implications. If effective, TF-CBT offers an EBP that can improve outcomes for high-need orphans in LAMICs. In addition, our research contributes to the growing body of literature on EBPs in LAMICs and extends other work in the task shifting area by incorporating trained lay counselors into both the training and supervision of a subsequent generation of lay counselors to increase local responsibility and sustainability.

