TF-CBT	80	80	80	80
Usual Care	80	80	80	80
Total by Country	320		320	
Total	640			

3C3. Study Conditions

3C3a. TF-CBT Condition. Children will receive the TF-CBT treatment protocol as tested in the TZ feasibility study and modified for KE (see 3C1c). [name], the KE-lay counselors, KE-based investigator ([name]), and the local trainers ([name], [name], & [name]) will oversee iterative modifications of the 12-week protocol that maintain fidelity and are culturally responsive and appropriate. A thorough overview of TF-CBT (Appendix D) and the TZ TF-CBT protocol (Appendix B) are included with this proposal and briefly described here. The intervention is delivered in 12 1.5-hour group sessions and 3 1-hour individual sessions, provided over 12 weeks. During weeks 1-8, guardian and child groups (8 participants in each) are run separately and concurrently with guardians and children earning the same skills. In the final 4 groups (groups 9-12) they participate in conjoint child-guardian activities. The trauma narrative, gradual exposure component is conducted in individual visits with the child (which are weekly and begin after group 4; see Appendix B), so that

the child can talk privately, one-on-one, with a counselor about the details, thoughts, and feelings related to their parent(s) death(s) and other traumatic events and so that other children are not triggered or traumatized by another child's narrative details. In groups 5-8, the children review, with counselor support, what they have done in the individual sessions (e.g., draw the picture again, write the story again), but no details are shared in the group. The group intervention is efficient (e.g., can provide treatment to 8 children-caregiver dyads with 3 counselors), culturally responsive (e.g., group delivery, modified analogies), and normalizing, as it includes other children/guardians with similar problems. The inclusion of the 3 individual sessions after trust is built, as with other group-based trauma treatment models⁹⁵ allows for individualization and privacy around specific trauma narrative details.

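### The end-of-treatment interview is timed from baseline, so an on-protocol interview can fall just before the last TF-CBT group session

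*Combined protocol and SAP*

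**What the plan says.** Section 3C4a sets the first follow-up at "12-14 weeks post-baseline (i.e., end of treatment for the TF-CBT condition, with a 2-week window". Section 3C4d repeats the baseline anchor for both arms: "All dyads are assessed again at 12-14 weeks post-baseline, 6-months, and 12-months post baseline". The Table 4 footnote defines the 12w label as the same 12 to 14 weeks.

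On treatment, section 3C4d says "Guardian-child dyads randomized to TF-CBT begin the 12-week group protocol within 2 weeks". Section 3C3a gives the length: "The intervention is delivered in 12 1.5-hour group sessions and 3 1-hour individual sessions, provided over 12 weeks". It also describes the last block: "In the final 4 groups (groups 9-12) they participate in conjoint child-guardian activities".

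On analysis, section 3C5b states the first test of Hypothesis 1 as "First, we test whether the TF-CBT condition differs from the UC condition at 12-weeks (i.e., end of TF-CBT", and section 3C5c calls the 12-week difference the primary hypothesis test. Table 4 puts the guardian exit interview, for TF-CBT only, at this same visit.

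**The concern.** The visit carries two definitions: a number of weeks since baseline, and the end of the TF-CBT course. They agree only if each interview is booked after that dyad's last session. Neither statement of visit timing requires this, and neither links a dyad's interview date to its start date.

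A late start is plausible. Groups hold 8 dyads, so families enrolled first may wait while a group fills. Children in one group then share a start date but have different baseline dates, and a window counted from baseline meets them at different points in the course.

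At stake is the meaning of the primary time point. An interview held too early can under-count exposure only in the TF-CBT arm, so the likely direction is dilution of the 12-week difference. A little treatment would also fall after the measure that is meant to mark its end. This slightly blurs the comparison with 6 and 12 months, where the plan asks whether gains are maintained. The exit interview could likewise come before the final session.

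**Working it through.** **Inputs**

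- Visit time t: 12 to 14 weeks after baseline (3C4a, 3C4d, Table 4 footnote).
- Start lag s: 0 to 2 weeks (3C4d). The order is "remaining baseline assessment measures are administered (see Table 4) and participants are randomized", with no interval stated between the two. I take that interval as zero.
- Course: 12 group sessions in 12 weeks (3C3a). I take these as weekly, so session k falls at s + (k − 1).

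**Step 1. Reproduce the plan's window.** Course end = s + 12, which runs from 0 + 12 = 12 to 2 + 12 = 14 weeks. This is exactly the stated window, so the window probably was chosen to absorb the start lag.

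**Step 2. Date of the last group session.** Session 12 falls at s + 11, from week 11 to week 13.

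**Step 3. Position of the interview relative to session 12.**

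| Start (s) | Session 12 | Visit at week 12 | Visit at week 13 | Visit at week 14 |
|---|---|---|---|---|
| 0 | week 11 | after | after | after |
| 1 | week 12 | same day | after | after |
| 2 | week 13 | 1 week before | same day | after |

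All nine combinations comply with the stated timing. One clearly precedes session 12, and two depend on the order of events that day.

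**Step 4. Bound on the shortfall.** Session 11 falls at s + 10, which is at most 2 + 10 = 12, so it is never later than the earliest allowed visit. At most one group session is outstanding. The one exception is s = 2 and t = 12 with the interview held before that day's session, when two are. The outstanding session belongs to the conjoint block (groups 9-12). The three individual sessions are weekly and begin after group 4, so they are finished by then. A postponed session, or a gap between baseline and randomization, would widen the shortfall.

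**Step 5. Share of TF-CBT visits affected (illustration).** Assume that s is uniform on 0 to 2, t is uniform on 12 to 14, and the two are independent. The documents do not give these distributions. The visit precedes session 12 when t < s + 11, which needs s > 1. For such s, P(t < s + 11) = (s − 1)/2. With density 1/2 for s:

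P = ∫ from 1 to 2 of (1/2) × (s − 1)/2 ds = (1/4) × (1/2) = 1/8 = 12.5%.

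A simulation of one million draws gave 12.48%. If visits are always booked after the last session, the share is zero.

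**Step 6. Average content missed.** 0.125 × 1/12 = 0.0104, or about 1% of scheduled group sessions across the TF-CBT arm. The documents give no effect per session, so this cannot be turned into a loss of effect size.

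**The case against.** The strongest reply is that the matching intervals show a plan that works. The visit is described as the end of treatment, the Aim 3 text in section 3C5b repeats that description, and an exit interview presupposes a finished course. On this reading a dyad starting at week 2 is simply seen near week 14. The Human Subjects section and the appendices to which the plan refers are not in the reviewed document and may contain booking instructions.

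Much of this stands. The intent is clear, and if sites follow it the shortfall is zero. But the operative rule is counted from baseline, and it permits an interview that contradicts the label. Section 3C4a keeps interviewers at minimal contact with counselors, and the reviewed text does not say how they would learn a group's last session date.

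Three stronger readings are tempting, and the documents do not support them.

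- **Half of TF-CBT children are interviewed before treatment ends.** Under the Step 5 assumptions, half of visits do precede s + 12, the end of 12 calendar weeks. With weekly sessions, however, nothing is scheduled between s + 11 and s + 12, so most of these children have had every session.
- **The depression score is compromised by its recall period.** Table 4 says "The MFQ has 13 items and assesses depressive symptoms over the past 2 weeks". Any visit soon after a last session has this overlap, and a later window does not fully remove it: session 12 at week 13 and a visit at week 14 still overlap.
- **Attendance for Aim 3 is tied to this visit.** Table 4 records attendance at each group, and section 3C4b has the counselors' reports sent within two days. Any session held after an interview could therefore be identified.

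**Conclusion.** The point holds as a small inconsistency at the primary time point. The plan's own dates allow a compliant primary-outcome interview, and the exit interview with it, to take place before the final group session. With weekly sessions on schedule the shortfall is bounded at about one session of 12. How many children are affected depends on booking practice that the documents do not describe, so the 12.5% is an illustration and not an estimate.

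The expected consequence is slight dilution of the 12-week contrast. A reader might infer that the primary comparison is invalid or seriously underestimates the effect; nothing in the documents supports that. The case for changing the text is that the definition should not contradict itself where the main test is made, and that the correction is nearly free.

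**What to change.** Leave the treatment schedule unchanged and reconcile the assessment timing in sections 3C4a, 3C4d and 3C5b and the Table 4 footnote:

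1. Use one post-baseline window for both arms that opens once the latest scheduled course end (2 + 12 = 14 weeks) has been reached, for example 14-16 weeks. A common window keeps timing comparable with usual care, which has no last session to count from.
2. Add that no TF-CBT interview, including the exit interview, is held before that group's final scheduled session. This covers postponed sessions, which a window counted from baseline cannot.
3. Change the 12-week wording of the primary comparison to match the new window.
4. Check compliance against session dates from the existing group reports. No new form is needed.

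The cost is mainly wording, with the same number of visits. Session 12 falls at weeks 11 to 13, so interviews would come from 14 − 13 = 1 week to 16 − 11 = 5 weeks after it, and early starters would be seen somewhat later than the end of treatment. The gap to the 6-month visit (about week 26) shortens by 2 weeks, from 12-14 weeks to 10-12 weeks. If postponed sessions push some TF-CBT interviews later, the arms would differ slightly in timing, so the interval from baseline to interview should be reported by arm.
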